#### Drug exposure period:

Randomized subjects will receive 12 days of study medication at the time of randomization. A riboflavin tracer (25 mg for 4.45 mg pill; 50 mg for 17.8 mg pill) will be added to each capsule to serve as an objective measure of medication adherence using urine obtained on the day of the alcohol challenge. Two bottles will be dispensed to each subject. One bottle will contain 14 pills of pitolisant (4.45 mg) or placebo and the other bottle will contain 5 pills of pitolisant (17.8 mg) or placebo. All pills will be over-encapsulated with 25 mg (4.45 mg pill) or 50 mg (17.8 mg pill) of riboflavin. Subjects will take an 8.9 mg dose (two 4.45 mg pills) of pitolisant or placebo

once per day on day 1 through 7. Subjects will then take a 17.8 mg dose (one 17.8 mg pill) of pitolisant or placebo once per day on day 8 through 12. The 17.8 mg pill will be overencapsulated with 50 mg of riboflavin. Based on the published half-life for pitolisant, subjects should reach steady state levels after 5 days of taking the 17.8 mg dose. This dosing plan is consistent with the FDA approved prescribing information for the treatment of narcolepsy.

During the twelve-day period of drug exposure, subjects will be asked to answer a medication compliance question each day by smartphone using the REDCap data capture App. In addition to assessing medication compliance, subjects will also be asked to rate their craving for alcohol each day using the alcohol VAS. Subjects will receive a \$5 reimbursement on each day they complete the VAS and answer the medication compliance question using the REDcap smartphone App. Sleep quality during the drug exposure period will also be assessed by having subjects complete items from the National Sleep Foundation Sleep Diary each day. Items to be completed will include daily reports on the total number of hours slept per night and on the number of times and number of minutes for awakening during the night.

### Medication Visit #2

After the 7-14 day washout period subjects will return to the lab to receive study medication prior to the alcohol challenge #2. Subjects will complete the same tests and interviews completed during the randomization visit (See appendix A for schedule of events). Based on the assessments at medication visit #2, subjects be discontinued for the following reasons: pregnancy, recreational drug use except for marijuana, evidence of non-compliance with study medication, suicidal thoughts or behavior, and use of a new medication that would make participation unsafe. Subjects will receive a 12-day supply of study medication and will be scheduled for the alcohol challenge #2. Subjects will be allowed to delay start of medication for up to 7 days after randomization in order to accommodate scheduling for the alcohol challenge trial.

Alcohol Challenge Trials 1 & 2: Subjects will return to the laboratory on day 12 of drug exposure for each medication trial to complete the alcohol challenge. For safety reasons, subjects will be asked to arrange transportation plans (no driving) prior each of the alcohol challenge trials. There will be a 7-14 day washout period between alcohol challenge Trial 1 and medication visit #2. The washout may extend to 14 days to accommodate the scheduling of the medication visit. Concomitant medications, urine drug screening, urine pregnancy testing, blood alcohol level will be assessed to determine eligibility to proceed with the challenge. Blood alcohol level must be 0.000 to continue with the study procedures. Urine collected for drug screening will be exposed to ultraviolet light as an objective test of medication compliance. If no fluorescence is observed in the urine sample the subject will be excluded from continuing with the challenge. Measures of drinking (TLFB) and cravings (OCDS, VAS and AUQ) will be collected to inform secondary outcomes. Subjects will be observed taking the morning dose of pitolisant (or placebo) on the day of the challenge (after compliance is confirmed via a urine screening). The peak plasma concentration of pitolisant should be reached approximately 60 minutes after administration. The alcohol self-administration session will begin no sooner than one hour after the administration of the observed 17.8 mg morning dose. The alcohol selfadministration will be conducted in the GCRU. The room will be a carpeted and furnished with

a lounge chair, side table and television which allows access to popular streaming entertainment (e.g., Netflix, YouTube). A small unobtrusive camera is placed in the room to allow for monitoring without study staff being present in the room. The room has ready access to a bathroom. The alcohol self-administration is divided into four segments: 1) a 5-minute segment for the priming dose, 2) a 40-minute segment for observing alcohol's effects, 3) a 60-minute segment of alcohol self-administration (Block1) and, 4) a second 60-minute segment of alcohol self-administration (Block1) and, 4) a second 60-minute segment of alcohol self-administration (Block1) and, 4) a second 60-minute segment of alcohol self-administration (Block2) [see figure 2 for the alcohol self-administration Procedure].

Priming dose. Subjects will be given a priming drink designed to increase the subject's blood alcohol level (BAL) to 0.03g/dl, using the alcohol of their choice that is 24% Alcohol By Volume (ABV) or greater. The volume of alcohol will be calculated

Figure 2: Alcohol Self-Administration Procedure						
Priming Dose 5 minutes Drink mixed to achieve BAL= 0.03g/dl	Observation 40 minutes Craving and intoxication measured in 10- minute intervals	Self-Administration Blocks 1 & 2 60 minutes each 4 drinks per block Each drink mixed to raise BAL 0.0125 g/dl				

using an online tool developed by UW-Madison

(http://dionysus.psych.wisc.edu/WebCMS/baccalc.htm) based on a formula described by Watson. The subjects will be asked to drink the priming drink over a period of 5 minutes. Part of the purpose of the priming drink is to normalize drinking in the laboratory.

Observation period. Subjects will be observed for 40 minutes following the priming dose of alcohol to allow for absorption of the alcohol. Cravings will be assessed using the AUQ and VAS and effect of pitolisant on stimulant effects of alcohol swill be assessed using the BAES every 10 minutes during the observation period.

Alcohol self administration Blocks 1 and 2. In each of the alcohol self-administration Blocks, subjects will be presented with four drinks, each mixed to raise their BAL 0.0125g/dl. They will be told that they can either consume the desired number of drinks over the following 60 minutes or they will receive the equivalent dollar amount of the cost of each drink (\$3.00) they did not consume before leaving the clinic. At the end of each 1 hour session the tray with the remaining drinks will be removed and the amount of alcohol remaining will be measured. Cravings will be assessed using the AUO and VAS and effect of pitolisant on stimulant effects of alcohol will be assessed using the BAES every 30 min during the self-administration blocks. Based on the rate of alcohol metabolism over the time of the trial, we anticipate that subjects who consumed every drink could reach a BAC of 0.09 to 0.13 g/dl depending upon differences in alcohol metobolism. Safety assessments will be completed (intoxication, sedation, adverse effects) prior to subjects leaving the laboratory. Subjects will be required to have a plan for transportation home that does not involve driving. Subjects will not be released until their blood alcohol level is  $\leq 0.04$  g/dl and they are not behaviorally impaired. After the second alcohol self-administration trial has been completed subjects will receive a copy of the NIAAA publication Rethinking Drinking and will be encouraged to review rethinking drinking materials online.

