In healthy volunteers who were moderate drinkers, enhanced bold signals in the striatal areas including the nucleus accumbens were found to correlate with stimulation ratings during alcohol infusion. This finding suggests that alcohol-induced stimulation involves activation of the brain linked to the reinforcing effects of many drugs of abuse. One group of investigators has found that heavy drinkers may be more sensitive to the stimulant effects of alcohol than are light drinkers as measured on the ascending limb of the blood alcohol curve and suggest that continued sensitivity to the stimulant effects of alcohol may be one of the factors that contributes to the continued alcohol consumption in AUD. Given the possible role of alcohol stimulant effects in facilitating drinking and that pitolisant has what can be construed as stimulant-like properties such as decreasing daytime sleepiness and in enhancing alertness, it is important to determine that this drug will not enhance the stimulating effects of alcohol in drinkers. We hypothesize that it will not for several reasons. Pitolisant as compared to psychomotor stimulants such as amphetamine does not increase the release of dopamine in the nucleus accumbens, which may play a key role in mediating the reinforcing effects of many drugs of abuse. Unlike psychomotor stimulants pitolisant is not self-administered by primates, an established animal model of abuse liability. More importantly, among people who use stimulants, drug liking and willingness to use the drug did not differ significantly between pitolisant and placebo. In this study we will examine whether pitolisant increases the stimulant effects of a priming drink of alcohol as assessed using the biphasic alcohol effects scale (BAES).

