include treatment and Time Block. Trial order will be used as covariate in these analyses to allow evaluation as to whether the order of treatments had a significant effect on the outcome. Appropriate covariance structures will be determined using
covariate in these analyses to allow evaluation as to whether the order of treatments had a significant effect on the outcome. Appropriate covariance structures will be determined using
order of treatments had a significant effect on the outcome. Appropriate covariance structures will be determined using
Appropriate covariance structures will be determined using
Akaikes information criteria to evaluate the best model fit.
Results analysis will be examined for both treatment effects and
the Treatment x Time Block interaction results.
2. Subjects will report Craving measures (AUQ and VAS) collected at 30-minute
lower levels of craving as intervals during the self-administration trials will be used to test
measured by the Visual the effect of pitolisant on alcohol craving. A mixed models
Analog Scale (VAS) and approach will be used to test for differences in craving between
the Alcohol Urge the pitolisant and placebo self-administration trials. Within-
questionnaire (AUQ) subject factors for this analysis will include Treatment and Time
during the pitolisant self- Block. Trial order will be used as covariate in these analyses to
administration trial allow evaluation as to whether the order of treatments has a
compared to the placebo significant effect on the outcome.
self-administration trial.
3. Subjects will BAES scores and BALs obtained during the 40-minute
experience no difference observation period and both of the 60-minute self-administration
in alcohol-induced blocks will be used to test the effect of pitolisant on the
stimulation, as measured stimulating effects of alcohol. A mixed model for repeated
on the BAES, after the measures approach will be used to test for differences between
consumption of the pitolisant and placebo on the stimulant BAES scores at each of
priming dose of alcohol the 10-minute observation intervals and 30-minute self-
when they are receiving administration intervals. This data will be analyzed with
pitolisant as compared to Treatment and Time used as within-subject factors.
when they are receiving
placebo.
5. Subjects will report The alcohol VAS, OCDS, and the TLFB measurements during
lower levels of alcohol the twelve-day period of drug exposure will be used to determine

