## 15. Appendix A: Schedule of Events

	Baseline (May be split over 2 visits)	Randomization	Trial 1	Dispense	Trial 2
Clinic Visit #	0	1	2	3	4
Drug compliance/accountability			X		X
Urine Pregnancy Test	X	X	X	X	X
Birth control assessment	X	X	X	X	
AEs	X	X	X	X	X
C-SSRS	X	X	X	X	X
Dispense medication/placebo		X		X	
Brief Telephone Interview		Mid-week call 3-4 days, 6-7 days, and 9-10 days after starting medication		Mid-week call 3-4 days, 6-7 days and 9- 10 days after starting medication	
Treatment Referral					X
TLFB (28 day at baseline)	X	X	Х	X	Х
VAS		X Daily during 12- day medication exposure period	X	X Daily during 12- day medication exposure period	X
OCDS		X Days 7 and 11 of medication exposure period	X	X Days 7 and 11 of medication exposure period	X
AUQ		X	X	X	X
BAES			X		X
National Sleep Foundation Sleep Diary		Daily during 12- day medication exposure period		Daily during 12- day medication exposure period	

A) Test for opioids, cocaine, amphetamines, methamphetamine, tetrahydrocannabinol (THC), barbiturates, oxycodone, buprenorphine, methadone and benzodiazepines.

B) If the baseline visit is split between two days, UDS, vitals, breathalyzer, and weight are to be taken at each visit.

16. Appendix B: Schedule of assessments during the alcohol challenge

	Observation	Self-admin Block1	Self-admin Block2
Assessment			
BAC	Every 10	Every 30	Every 30
	minutes	minutes	minutes
VAS a)	Every 10	Every 30	Every 30
	minutes	minutes	minutes
AUQ		Every 30 minutes	Every 30 minutes
BAES	Every 10	Every 30	Every 30
	minutes	minutes	minutes

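### No BAES reading is scheduled before the priming drink, so hypothesis 3 cannot separate pitolisant's own stimulant effect from a change in alcohol-induced stimulation

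*Combined protocol and SAP*

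**What the plan says.** Section 3.1 gives the reason for measuring stimulation. It states that "pitolisant has what can be construed as stimulant-like properties such as decreasing daytime sleepiness and in enhancing alertness", and concludes that the trial must check that the drug does not add to alcohol's stimulation. Section 4.2.2 makes this a secondary outcome, measured with the BAES.

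The BAES timing is set in Section 9 and Appendix B:

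- **Observation period:** stimulation is "assessed using the BAES every 10 minutes during the observation period". That period comes after the drink: "Subjects will be observed for 40 minutes following the priming dose of alcohol to allow for absorption of the alcohol".
- **Blocks 1 and 2:** stimulation is "assessed using the BAES every 30 min during the self-administration blocks".
- **Before the session:** under Alcohol Challenge Trials 1 & 2, "Measures of drinking (TLFB) and cravings (OCDS, VAS and AUQ) will be collected to inform secondary outcomes". BAES is not in that list.
- **Between dose and session:** "The alcohol self-administration session will begin no sooner than one hour after the administration of the observed 17.8 mg morning dose". No BAES is placed in this gap.
- **Appendix B** ("Schedule of assessments during the alcohol challenge") has columns for observation, Block 1 and Block 2 only. Appendix A marks BAES at Trials 1 and 2, without a clock time, and at no other visit.

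For hypothesis 3, Section 12.1 uses BAES scores and BALs from the observation period and both blocks. It compares "pitolisant and placebo on the stimulant BAES scores at each of" the 10-minute and 30-minute intervals, with Treatment and Time as within-subject factors. It names no pre-drink term and does not say how BAL enters.

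**The concern.** The hypothesis is about what alcohol does to stimulation and whether pitolisant alters it. The protocol gives a drug that it describes as alerting, then takes every scheduled stimulation reading after alcohol. The crossover placebo removes alcohol's average effect from the contrast, but it does not remove the drug's own effect.

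Two errors become possible, in opposite directions. A drug that raises alertness items by itself could look as if it enhances alcohol's stimulation. A drug that raises resting stimulation but blunts the response to alcohol could show no net difference, which is the result that hypothesis 3 predicts. Either error would bear on how pitolisant is judged as a candidate for a later trial. A missing sober reading cannot be recovered once a session has been run.

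**Working it through.** **The plan's own figure.** Section 12.2 sizes the trial for alcohol consumption, not BAES: 28 completers, effect size 0.7, alpha 0.01, power 0.81. A paired t-test by the noncentral t with n = 28, d = 0.7 and two-sided alpha 0.01 gives power 0.815, so the figure reproduces. It does not bear on this point except to supply n = 28. The documents give no SD, alpha, margin or power for BAES.

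**What the planned contrast estimates.** Let d0 be pitolisant's own shift in stimulant BAES without alcohol, and i the change that it makes to the response to alcohol. If the two add:

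- post-drink difference, pitolisant minus placebo = d0 + i
- pre-drink difference, pitolisant minus placebo = d0 (not scheduled)
- difference in change from pre-drink = (d0 + i) − d0 = i, if d0 is stable over the session

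The plan observes only the first line: two unknowns, one contrast. For example, d0 = +0.5 and i = −0.5 give 0.5 − 0.5 = 0, and the blunting is hidden.

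**Number of readings affected.** If readings fall at the end of each interval, there are 40/10 = 4 in the observation period and 60/30 = 2 in each block, so 4 + 2 + 2 = 8. The documents do not say whether a reading is taken at minute 0 of a segment. A minute-0 reading in the observation period would still follow the 5-minute drink.

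**Size of a false signal (illustration).** Assume n = 28, two-sided alpha 0.05, i = 0, and d0 in SDs of the paired post-drink difference. The noncentrality is d0 × √28.

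| d0 | Probability that the post-drink test rejects no difference |
|---|---|
| 0 | 0.05 |
| 0.2 | 0.18 |
| 0.3 | 0.33 |
| 0.5 | 0.72 |
| 0.7 | 0.95 |

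With a stable d0, the change-from-pre-drink contrast stays at 0.05 in every row.

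**Precision cost of the change score.** Let r be the correlation between the pre-drink and post-drink paired differences, and assume equal variances. The SD of the change relative to the post-drink difference is √(2(1 − r)). Power is for i = 0.5.

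| r (assumed) | SD ratio | Power, change score |
|---|---|---|
| 0.3 | 1.183 | 0.58 |
| 0.5 | 1.000 | 0.72 |
| 0.7 | 0.775 | 0.91 |
| 0.8 | 0.632 | 0.98 |

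The post-drink test has power 0.72 for the same effect when d0 = 0. The change score therefore loses precision below r = 0.5 and gains above it.

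**Why covariate adjustment alone is not enough.** The pre-drink reading is taken on drug, so it contains d0. Adjusting with slope b removes only b × d0 and leaves (1 − b) × d0. With equal variances b = r, so for d0 = 0.5 the remainder is 0.7 × 0.5 = 0.35 at r = 0.3, 0.5 × 0.5 = 0.25 at r = 0.5, and 0.3 × 0.5 = 0.15 at r = 0.7.

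**The case against.** **BAL is recorded with BAES and named in the analysis.** Readings along a changing BAL carry some information on the alcohol slope as against a constant drug offset. This stands in part. But Section 12.1 does not say how BAL enters, and separating the two would mean extrapolating to zero alcohol. In the blocks the subject chooses the intake, and hypothesis 1 expects it to differ by treatment.

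**Total stimulation may be what matters.** Section 3.1 worries that stimulation promotes drinking. If drug plus alcohol together do not raise BAES, much of that worry is met however the total divides. This is fair, and the raw post-drink difference is worth reporting. It is not the quantity that hypothesis 3 names.

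**The drug's own effect may be small.** Section 3.1 also cites no rise in accumbens dopamine, no self-administration by primates, and no significant difference from placebo in drug liking. This limits how large d0 is likely to be. None of it is a BAES measurement, and the same section concedes alerting effects.

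**Some of the evidence of absence is weak.** The pre-session list covers drinking and craving, and BAES is neither. Appendix B also omits the pre-session VAS and AUQ. Appendix A gives no clock time. A reader might infer that BAES is never taken before alcohol; the documents support only that no such reading is scheduled or used in the analysis.

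**Conclusion.** The point holds as a gap in a secondary outcome. No pre-drink BAES is scheduled, and the planned hypothesis 3 contrast estimates d0 + i rather than i. The bias equals d0 if the effects add. The documents give no value for d0, and it may be zero, but the plan cannot show that. The rejection probabilities of 0.18 to 0.95 rest on an assumed alpha of 0.05, 28 completers and assumed shifts of 0.2 to 0.7 SD; they are not predictions.

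A reader might go further and infer that the trial will report a false enhancement, or that its stimulation question goes wholly unanswered. The documents do not support either reading: the first depends on an unknown d0, and the planned data still describe total stimulation under drug plus alcohol. The primary outcomes of consumption and craving, and the sample size, are unaffected.

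**What to change.** - **Section 9 and Appendix B:** in both trials, add one BAES after the observed dose and immediately before the priming drink, with a pre-drink column in Appendix B. The existing gap of at least one hour has room for it.
- **Section 12.1, hypothesis 3:** analyse stimulant BAES as change from that reading, or equivalently through a Treatment by pre/post term. Give most weight to the observation period, where the alcohol dose is fixed. State how BAL is used.
- **Reporting:** give the pre-drink treatment difference separately as the drug's own effect, and the raw post-drink difference as total stimulation.
- **Do not** enter the pre-drink reading only as a covariate, since part of d0 would remain.
- **If the reading cannot be added,** reword hypothesis 3 as total stimulation under drug plus alcohol.

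The cost is a minute or two per session for a scale already given repeatedly, and some loss of precision if r is below about 0.5. The change score also assumes that the drug's own effect is roughly stable over the session. That deserves a stated caveat: Section 9 puts peak plasma concentration about 60 minutes after the dose, and the session then runs 5 + 40 + 60 + 60 = 165 minutes. This is a further reason to favour the observation period.

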#### Subject compensation

Subjects will be compensated up to \$543 for completion of all study activities. Subjects will

receive a reimbursement of \$50 for the screening visit, \$100 for alcohol Challenge Trial #1, \$100 for alcohol Challenge Trial #2 and a \$75 completion bonus if they complete both challenges. Subjects will also receive \$20 on each of the two visits during which medication is dispensed. Subjects will receive a \$5 payment each on day during the two drug exposure periods that they respond to the REDcap smartphone app to rate their alcohol craving, medication compliance, and sleep quality. Subjects will also receive a \$10 completion bonus in each challenge if they complete the craving scale and medication log on all days. Subjects may receive up to \$48 dollars in payments for drinks not consumed during the two alcohol self-administration trials.

In addition to this \$543 of compensation, subject may also be reimbursed up to an additional \$60 for distributing study recruitment materials to other people who may want to take part in this study. Distributing recruitment materials is completely optional. subjects may take part in the study and decline to hand out flyers to people they know.

Subjects who report no recreational drug use other than marijuana at the time of phone screening but then test positive for recreational drug use other than marijuana at the first in-clinic visit will not be reimbursed. Subjects will be informed of this policy at the time of telephone screening. This measure is in place to prevent subjects from lying about no recreational drug use in order to receive compensation for a single visit in this study.

10 Assessment of Safety and Data Safety Monitoring Plan (DSMP)

